8.4 Rehabilitation

A history of prior rehabilitation therapy (e.g. physiotherapy, aerobic exercise) will be collected by the investigator or the site staff and recorded in the eCRF. This will include information about the type (e.g. treadmill, nordic walking), frequency (hours/week) and duration of the rehabilitation performed by the patient until the Screening Visit.

In addition, concurrent rehabilitation for the CPt arm will be collected using the Conventional Physiotherapy Tracking Sheet (Appendix F) in an electronic form from the signature of the ICF until EOS, including the type and frequency of the rehabilitation performed.

8.5 Device Deficiencies and Complaints

Device deficiency is the inadequacy of a medical device with respect to its identity, quality, durability, reliability, usability, safety or performance. Device deficiencies include malfunctions, use errors, and inadequacy in the information supplied by the manufacturer, including labelling.

All device deficiencies of the investigational device will be documented throughout the study by the Investigator on a dedicated form provided or by the Sponsor directly. The Sponsor is responsible for managing the deficiencies in accordance with written procedures for the control of a non-conforming product and complying with the reporting rules to authorities. The Sponsor will take, where applicable, appropriate corrective and preventive actions to protect the safety of subjects, users, and other persons. The Sponsor will arrange for the safe return of the investigational device that is related to the device deficiency.

Any device deficiencies resulting in a safety event must be recorded as an adverse event indicating the relatedness.

Complaints regarding the usability of the device coming either from the patient or the site staff will be documented on the dedicated form and will be provided to the Sponsor for evaluation on a regular basis.

8.6 Clinical Scales

Clinical scales will be either completed during site visits or remotely by the patient in a paper format which will serve as a source document. Sub- and/or final scores will be recorded in the eCRF.

8.6.1 Montreal Cognitive Assessment (MoCA)

The Montreal cognitive assessment is a widely used clinical screening assessment designed to evaluate cognitive impairment (Nasreddine et al., 2005). The MoCA consists of 16 items belonging to multiple cognitive domains (visuo-spatial and executive functions, naming, memory, attention, language, abstraction and orientation). Each element is scored according to its individual procedure to yield a total score ranging from 0 to 30, where lower numbers indicate worse cognitive performance. The neurologist administers the assessment and performs the scoring. The MoCA takes approximately 10 minutes to complete.

The MoCA will be performed at Screening (Appendix K).

8.6.2 Modified Hoehn and Yahr staging (mH&Y)

The modified Hoehn and Yahr scale is a standard clinical rating scale, designed to evaluate the progression and level of functional disability associated with Parkinson's disease and Parkinsonism in a clinical setting (Hoehn and Yahr, 1967). The Hoehn and Yahr scale consists of seven stages describing the extent and impact of symptoms (Goetz et al., 2004). The Investigator performs an interview and a medical examination aimed at evaluating the extent of the patient's symptoms and functional disability. The Investigator scores the stage based on the clinical criteria, where a higher stage value indicates more severe symptoms. The Hoehn and Yahr staging takes approximately 15 minutes to complete.

The mH&Y staging will be performed at Screening and at Visit 4 (Appendix N).

8.6.3 The Movement Disorder Society sponsored Revision of the Unified Parkinson's Disease Rating Scale (MDS-UPDRS)

The Movement Disorder Society sponsored Revision of the Unified Parkinson's Disease Rating Scale (MDS-UPDRS) is a comprehensive assessment of the Non-Motor aspects of Experiences of Daily living (nM-EDL), Activities of Daily Living (ADL), motor symptoms and motor complications of Parkinson's Disease (Goetz et al., 2008). The MDS-UPDRS Part I is a clinician rated (question 1-6) and patient self-reported scale (question 7-13) consisting of 13 questions about Non-Motor aspects of daily living; Part II is a patient self-rated scale consisting of 13 questions about ADLs; Part III is a clinician-rated scale consisting of 18 neurological motor examinations and part IV is a clinician rated scale consisting of 6 motor examinations evaluating dyskinesias and motor fluctuations. All sections are scored on a five point interval scale ranging from 0 (absence of impact) to 4 (most severe impact). Part I is administered partly by the Investigator and partly self-reported by the patient or caregiver; Part II and IV are administered by the Investigator. The MDS-UPDRS takes overall approximately 35 minutes to complete.

The MDS-UPDRS will be performed on site at Baseline Visit, Visit 3 and Visit 4 (Appendix M).

8.6.4 Parkinson's Disease Questionnaire (PDQ-39)

The Parkinson's Disease Questionnaire is a reliable patient self-rated scale, designed to evaluate the impact of disease on quality of life in Parkinson's patients (Peto et al., 1995). The PDQ-39 consists of 39 questions divided in eight dimensions corresponding to different aspects of daily life (mobility, activities of daily living, emotional well-being, stigma, social support, cognition, communication, and bodily discomfort). The questions are scored on a five point interval scale ranging from 0 (absence of impact) to 4 (most severe impact). The individual scores of each dimension are subsequently summed to yield a total, where higher values indicate a more severe impact on that aspect of the patient's life. This test is self-administered by the patient. The PDQ-39 takes approximately ten minutes to complete.

The PDQ-39 will be performed on site at Baseline Visit, Visit 3 and Visit 4 (Appendix I).

8.6.5 Parkinson's Disease Questionnaire (PDQ-8)

The Parkinson's Disease Questionnaire is a short-form patient self-rated scale derived from the PDQ-39, designed to quickly evaluate the impact of disease on quality of life in Parkinson's patients (Jenkinson et al., 1997). The PDQ-8 was created by selecting the one question in each of the eight dimensions of PDQ-39 which had the highest correlation with the final sub score of that dimension (Mobility, activities of daily living, emotional well-being, stigma, social support, cognition, communication and bodily discomfort). The PDQ-8 therefore consists of eight questions, each already present in the original PDQ-39 and representing all dimensions. The questions are scored on a five point interval scale ranging from 0 (absence of issue) to 4 (issue always present). The individual scores of each dimension are subsequently summed to yield a total, which is reported as a percentage of the total possible score, where higher percentage values indicate a more severe impact on that aspect of the patient's life. This test is self-administered by the patient. The PDQ-8 takes approximately five minutes to complete.

The PDQ-8 will be performed remotely at Visit 1, Visit 2, Visit 1.1 and Visit 2.1 (Appendix J).

8.6.6 Clinical Global Impression of Severity (CGI-S)

The Clinical Global Impression of Severity is a standard clinician rating scale commonly used in Parkinsonism clinical trials, designed to assess the severity of symptoms of a patient (Guy, 1976). The CGI-S consists of a single assessment, scored on a scale ranging from 1 (normal/least severe symptoms) to 7 (most severe symptoms). The Investigator performs a medical examination and the scoring. The CGI-S takes around three minutes to complete.

The CGI-S will be performed at the Baseline Visit (Appendix R).

8.6.7 Patient Global Impression of Severity (PGI-S)

The Patient Global Impression of Severity is a standard patient self-rated scale, designed to evaluate the severity of symptoms of a patient (Guy, 1976). The PGI-S consists of a single assessment, scored on a scale ranging from 1 (normal/least severe symptoms) to 7 (most severe symptoms). This assessment is self-administered by the patient. The PGI-S takes approximately three minutes to complete.

The PGI-S will be performed at the Baseline Visit (Appendix Q).

8.6.8 Clinical Global Impression of Improvement (CGI-I)

The Clinical Global Impression of Improvement is a standard clinician rating scale commonly used in Parkinsonism clinical trials, designed to assess the patient's improvement over a period of time (Guy, 1976). The CGI-I consists of a single assessment, scored on a scale ranging from 1 (very much improved) to 7 (very much worse). The investigator performs a medical examination and the scoring. The CGI-I takes around three minutes to complete.

The CGI-I will be performed at Visit 3 and Visit 4 (Appendix R).

8.6.9 Patient Global Impression of Improvement (PGI-I)

The Patient Global Impression of Improvement is a standard patient self-rated scale, designed to evaluate the improvement of the patient's condition over a defined period of time from his/her own perception (Yalcin and Bump, 2003). The PGI-I consists of a single assessment, scored on a scale ranging from 1 (normal/least severe symptoms) to 4 (most severe symptoms). This assessment is self-administered by the patient. The PGI-I takes approximately three minutes to complete.

The PGI-I will be performed at Visit 3 and Visit 4 (Appendix Q).

8.6.10 Parkinson Disease Sleep Scale 2 (PDSS-2)

The Parkinson Disease Sleep Scale 2 is a reliable instrument for quantifying sleep disruption in Parkinson's Disease patients (Chaudhuri, 2002). The PDSS-2 consists of 15 questions, addressing the frequency of sleep-related difficulties and disturbances. The PDSS-2 is scored on a 11-point interval scale ranging from 0 (most frequent presence of sleep disturbances) to 10 (absence of sleep disturbances). The individual scores are subsequently summed to yield a total score ranging from 0 to 150. This test is self-administered by the patient. The PDSS-2 test takes approximately five minutes to complete.

The PDSS-2 will be performed at the site during the Baseline Visit, Visit 3 and Visit 4 and remotely during Visit 1, Visit 2, Visit 1.1 and Visit 2.1 (Appendix P).

8.6.11 Pain Visual Analog scale (VAS)

The pain Visual Analog Scale is a standard patient rating scale, commonly used to evaluate the intensity of pain experienced by the patient. The pain VAS consists of a unidimensional graduated segment indicating pain in the form of numbers from 0 (no pain) to 10 (maximum imaginable pain). The pain VAS is therefore scored on a 11-point interval scale ranging from 0 to 10. This test is self administered by the patient. The pain VAS takes approximately 3 minutes to complete.

The Pain VAS will be performed at the site during the Baseline Visit, Visit 3 and Visit 4 and remotely during Visit 1, Visit 2, Visit 1.1 and Visit 2.1 (Appendix H).

8.6.12 Freezing of gait questionnaire (FOG-Q)

The Freezing of gait questionnaire is a patient self-rated, investigator administered scale designed to evaluate freezing of gait in patients with Parkinson's disease or Parkinsonism (Giladi et al., 2000). The FOG-Q consists of six questions scored on a five point interval scale ranging from 0 (absence of symptoms) to 4 (most severe symptoms). The individual scores are subsequently summed to yield a total score ranging from 0 to 24, where higher scores indicate a more severe freezing of gait. The FOG-Q test takes approximately five minutes to complete.

The FOG-Q will be performed at Baseline Visit, Visit 3 and Visit 4 (Appendix O).

8.7 Falls Diary

Patients have to keep a falls diary throughout their participation in the study by registering falls and near falls, as described in Appendix G. They will need to bring their diaries to the site visits so the data can be registered in the database.

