	Change from baseline to Week 12 (Visit 3) in Stance Time Variability assessed during the 6MWT.
	Secondary Endpoints
	• Rate of falls at Week 12 based on the results of the falls diary.
	• Change from baseline to Week 12 (Visit 3) in the asymmetry of the swing duration assessed during the 6MWT.
	• Change from baseline to Week 12 (Visit 3) in the Mini-BESTest.
	• Change from baseline to Week 12 (Visit 3) in Unified Parkinson's Disease Rating Scale (MDS-UPDRS) Part III sub-score.
	• Change from baseline to Week 12 (Visit 3) in the results of the Parkinson Disease Questionnaire (PDQ-39).
	Exploratory Endpoints
	• Rate of falls at Week 24 based on the results of the falls diary.
	• Change from Baseline to Week 24 (Visit 4) and from Week 12 (Visit 3) to Week 24 in:
	- Gait velocity (cm/s) assessed during the 6MWT
	- Stance Time Variability assessed during the 6MWT
	- Asymmetry of the swing duration assessed during 6MWT
	- the Mini-BESTest
	- MDS-UPDRS Part III sub-score
	- the results of the PDQ-39
	 Change from Baseline to Week 12 (Visit 3) and to Week 24 (Visit 4) and from Week 12 to Week 24 in the:
	- gait parameters measured by the FeetMe Monitor during the 6MWTs other than ones of the primary and secondary endpoints
	- gait parameters measured by the FeetMe Monitor during remote gait monitoring
	- results of the pain VAS
	- results of the Parkinson Disease Sleep Scale 2 (PDSS2)
	- results of the Clinical and Patient Global Impression of Severity scales (CGI/PGI-S)
	- results of the Clinical and Patient Global Impression of Improvement scales (CGI/PGI-I)
	• results of the MDS-UPDRS I, II and IV sub scores
	• Actual versus prescribed time spent on physiotherapy at Week 12 and Week 24.
· · · · · · · · · · · · · · · · · · ·	

	• Results of the Patient and Investigator satisfaction questionnaire.
	• Number of device and protocol procedure related adverse events at Week 12 and at Week 24.

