7.4 Primary Intervention Period

Following the Baseline Visit, all patients will begin their 12-week physiotherapy (or no-physiotherapy) regimen according to their randomisation.

During this period:

- All patients will participate in the Remote Gait Monitoring 1 and Visits 1-3 (Sections 7.3.1, 7.3.2, 7.3.3).
- Patients on the Conventional Physiotherapy arm, if they have access to it will start or continue their conventional physiotherapy and will keep track of it using the Conventional Physiotherapy Tracking Sheet (Appendix F). Patients who did not have access to CPt at the time of inclusion but manage to arrange one during the Primary Intervention Period will restart their PIP.
- On the other arm patients will start the FeetMe rehabilitation program (Section 4.4, Appendix A and B).
- In addition, all patients will keep a falls diary (Appendix G).

7.4.1 Remote Gait Monitoring 1

At the end of the Baseline Visit, all patients will take the FeetMe Insoles, mobile devices and chargers with them to their homes. A Patient User Guide will be provided.

- All patients will use the insoles remotely while performing their day-to-day activities (including physiotherapy) for two weeks. Data will be recorded in standalone mode (without a phone).
- Patients will download the data from the insoles at the end of each day.

7.4.2 Visits 1 and 2

Four and eight weeks after Baseline Visit, two remote visits (Visit 1 and 2) will take place. Patients will be asked to fill in the following questionnaires:

- PDSS-2
- Pain VAS
- Parkinson Disease Questionnaire, Short Form (PDQ-8).

7.4.3 Visit 3

Twelve weeks after Baseline Visit, that is, at the end of the 12-week Primary Intervention Period, all patients will participate in an in-clinic visit (Visit 3), where they will perform the same series of assessments as in the Baseline Visit. Patients will need to bring their FeetMe devices, their diaries, trackers and filled-in questionnaires to the visit.

The following assessments will be performed at Visit 3:

- Gait Assessments, which must be performed in the ON-phase:
 - 6 Minutes Walk Tests (6MWT)
 - Mini-BESTest.

During the 6MWT and the Mini-BESTest patients must wear the insoles. Specific instructions set out in the Site User Manual must be followed when setting up and executing the assessments.

- Disease specific rating scales:
 - MDS-UPDRS
- Other Assessments:
 - FOG-Q
 - PDSS2
 - Pain VAS
 - PDQ39

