 - Clinical Global Impression of Improvement / Patient Global Impression of Improvement (CGI/PGI-I)
- Potential adverse events and change in concomitant medication since the last contact.
- The source documents must be collected from the patients and the diary and tracker transcribed into the database.
- Also, the patients further allocation is to be decided (Section 7.4).
- At the end of the visit the patients will return home with their devices (as applicable based on their new or unchanged treatment) and proceed into the Remote Gait Monitoring 2 (Section 7.4.1).

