7.7 Withdrawal / Early Termination Visit

Patients may withdraw from the study at any time at their request or following a decision of the Investigator or Sponsor. In case of termination due to a patient's decision, every effort should be made to determine the primary reason for withdrawal and to document it in the eCRF.

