
9.5.2 Analysis for the secondary endpoints

The statistical method described for the primary objective will be used for the analysis of the following secondary endpoints:

- Change from baseline to Week 12 (Visit 3) in Stance Time Variability assessed during the 6 Minutes Walk Test (6MWT).
- Change from baseline to Week 12 (Visit 3) in the asymmetry of the swing duration assessed during the 6 Minutes Walk Test (6MWT).
- Change from baseline to Week 12 (Visit 3) in the MiniBESTest.
- Change from baseline to Week 12 (Visit 3) in MDS-UPDRS part III sub-score.
- Change from baseline to Week 12 (Visit 3) the results of the Parkinson Disease Questionnaire (PDQ-39)

The rate of falls during the primary intervention period will be compared between the 2 groups using a generalized linear model (GLM with log link function and negative binomial distribution) with the logarithm of duration of patient's follow up (censored at week 12) as offset variable. Effect size will be estimated by the relative risk ((Feetme rehabilitation versus conventional rehabilitation) and it's 95% confidence interval from the using GLM model.

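### The falls diary has no stated collection point before Visit 3 or at withdrawal, so patients who leave before Week 12 will probably lack the partial records that the falls model presumes

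*Protocol*

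**What the plan says.** The Synopsis and Table 5.1 list, as a secondary endpoint, "Rate of falls at Week 12 based on the results of the falls diary". The diary is therefore the named data source.

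Section 8.7 gives the route to the database: "They will need to bring their diaries to the site visits so the data can be registered in the database". Between baseline and Week 12 no site visit is planned. Section 7.4.2 reads "Four and eight weeks after Baseline Visit, two remote visits (Visit 1 and 2) will take place" and then "Patients will be asked to fill in the following questionnaires", followed by PDSS-2, pain VAS and PDQ-8. The diary first appears at Visit 3, in section 7.4.3: "Patients will need to bring their FeetMe devices, their diaries, trackers and filled-in questionnaires to the visit", and later in the same list "The source documents must be collected from the patients and the diary and tracker transcribed into the database". Section 7.5.3 repeats the transcription step for Visit 4.

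Section 7.7 has a title that names an early termination visit. Its text asks only that, when a patient decides to stop, "every effort should be made to determine the primary reason for withdrawal and to document it in the eCRF". It schedules no assessment and no return of the diary.

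For the analysis, section 9.5.2 specifies a negative binomial model with log link "with the logarithm of duration of patient's follow up (censored at week 12) as offset variable". Sections 9.1 and 9.1.1 place efficacy analyses on the FAS, that is, everyone randomised with a baseline gait measurement. Patients who leave early belong to it.

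**The concern.** An offset for follow-up time lets a patient observed for seven weeks contribute seven weeks of falls. That works only if both the falls and the time at risk over those weeks are known. As the procedures are written, the time to withdrawal will be known, but the falls record stays in a paper diary at the patient's home.

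The loss is unlikely to be random. Patients who leave because of an injury or worsening disease may well have fallen more than those who stay. Reducing fall risk is one of the programme's stated aims (section 4.2.2), so the falls comparison will be read closely even though it is a secondary endpoint. Falls that were never collected cannot be recovered by any later analysis plan.

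**Working it through.** **Inputs from the Protocol (section 9.4).** 75 patients per arm, 150 in total. Dropout of 20% for the Week 12 gait velocity measurement, made up of 15% for loss to follow-up and 5% for death or injury. No sample size or power is given for falls.

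**The plan's own figure.** A difference of 14 cm/s, SD 27 cm/s, two-sided alpha 0.05 and 80% power give 59.4 per group with a two-sample t-test, rounded up to 60. Then 60 / (1 − 0.20) = 75. The stated 60 and 75 reproduce.

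**Assumptions (not in the Protocol).** Mean week of exit, taken as 3, 6 or 9. The leavers' fall rate as a multiple *k* of the completers' rate, taken as 1.5, 2 or 3. Unequal dropout between arms, taken as 10% and 30%.

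**Step 1: how much diary time could be missing.** Leavers: 0.20 × 150 = 30. Completers contribute 120 × 12 = 1440 person-weeks.

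| Mean exit week | Leavers' person-weeks | Share of total |
|---|---|---|
| 3 | 30 × 3 = 90 | 90 / 1530 = 5.9% |
| 6 | 30 × 6 = 180 | 180 / 1620 = 11.1% |
| 9 | 30 × 9 = 270 | 270 / 1710 = 15.8% |

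Counting only the 15% lost to follow-up (22.5 patients, completers 127.5 × 12 = 1530), the share runs from 67.5 / 1597.5 = 4.2% to 202.5 / 1732.5 = 11.7%.

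**Step 2: effect on the rate within an arm.** Set the completers' rate to 1. With dropout *d* and mean exit at week 6, the rate using all diary time up to exit is

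[(1 − d) × 12 + d × 6 × k] / [(1 − d) × 12 + d × 6].

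With d = 0.20 this is (9.6 + 1.2k) / 10.8:

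- k = 1.5: 11.4 / 10.8 = 1.056; the completer-only rate of 1 is 5.3% low.
- k = 2: 12.0 / 10.8 = 1.111; 10.0% low.
- k = 3: 13.2 / 10.8 = 1.222; 18.2% low.

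**Step 3: effect on the rate ratio.** The completers' ratio is set to 1.00.

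- Same dropout and same *k* in both arms: the factor cancels, and the all-data ratio is also 1.00. There is no bias.
- Dropout 10% FeetMe and 30% control, k = 2: (10.8 + 1.2) / 11.4 = 1.053 and (8.4 + 3.6) / 10.2 = 1.176. The ratio is 1.053 / 1.176 = 0.895, which reads as 1.00 in completers.
- Dropout reversed: 1.118, which reads as 1.00.
- Range under the same 10% and 30%: 0.943 or 1.060 with k = 1.5; 0.817 or 1.224 with k = 3.
- Equal 20% dropout but k = 1.5 in one arm and 3 in the other: 11.4 / 13.2 = 0.864, which reads as 1.00.

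**The case against.** The strongest reply is that the Protocol leaves a step unspecified; it does not state that data will be lost. Several parts of this stand.

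- **Falls have a second route.** Section 8.9.3 names falls among adverse events of special interest, and section 8.9 collects these from consent to the end of participation. A reader might infer that early leavers have no falls data at all; the documents do not support that. The route does not rescue the endpoint, though. Adverse events are not its stated source, and section 7.4.2 lists no adverse event enquiry at Visits 1 and 2. The calls in section 4.4 that log potential adverse events, weekly and then every two weeks, are described only for patients on the FeetMe programme. Filling gaps from that source would make ascertainment differ by arm.
- **Loss is not certain for every leaver.** Nothing forbids returning a diary after withdrawal, and section 7.7 names a visit even if it gives it no content. A patient who misses Visit 3 but attends Visit 4 can still supply weeks 0 to 12. Someone who stops treatment but stays in the study still attends Visit 3. An analysis of strict completers is therefore a likely result, not a stated rule.
- **The 20% is not a diary-loss rate.** It is dropout for the gait measurement. An injured patient who cannot do the walk test may still hand in a diary. It serves here as an upper figure.
- **Scoring leavers as having had no falls is not planned anywhere.** Appendix G has one row per event date, with no field for the period covered and no way to record a fall-free period. An unreturned diary can thus look like a fall-free one. That is a hazard to close, not a rule in the plan.
- **Defining follow-up time can be left to the SAP.** That is fair, since section 9 assigns derivations to it. The SAP cannot supply records that were never collected.

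**Conclusion.** The point holds as a gap between collection and analysis. Followed as written, the procedures give no means of obtaining diary data from patients who leave before Week 12, while the offset model on the FAS presumes those partial records.

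Up to about 30 of 150 patients could be affected. Under the assumed exit times, that is about 6% to 16% of person-time. The within-arm rate would be about 5% to 18% low if leavers fall 1.5 to 3 times as often as completers and leave on average at week 6.

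A reader might go further and infer that the relative risk is biased. The documents do not show this. Bias in the ratio requires dropout, or leavers' relative fall rates, to differ between arms, and the Protocol gives no figure for either. The 0.895 and 1.118 examples show what could happen under stated assumptions and are not predictions.

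The falls rate is a non-key secondary endpoint outside the confirmatory hierarchy of section 9.2.2, so the primary conclusion is not touched. The change is still worth making, because it is cheap now and impossible once patients have left.

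**What to change.** - **Sections 7.4.2 and 8.7:** at the existing remote Visits 1 and 2, record in the eCRF the diary entries since the last contact, with dates, and an explicit statement when there were none. Do this identically in both arms.
- **Section 7.7:** retrieve the diary up to the date of withdrawal, by visit, phone or post.
- **Section 9.5.2:** define the offset as the log of the time covered by diary data, up to Week 12, not the time to withdrawal.

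The cost is a few minutes at two contacts that already take place, plus one eCRF form. No new visit is needed.
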